Sessions will be interspaced with days when the programmer and engineer will address issues uncovered in the previous session(s). The process will be repeated in the subsequent 2 weeks with the other 2 volunteers. The Usability study will inform improvements necessary in the BAC system prior to feasibility study.

Feasibility Study (PowerBack Rehabilitation)

This will be an ABA protocol, with measures taken pre- (A), during experimental therapy (B) and post-intervention (A).

Participants Recruitment

6 elderly sub-acute post-CVA admitted to PowerBack for inpatient rehabilitation will be recruited. Participants will be pre-screened through a script questionnaire and MoCA screening. Those who met inclusion criteria will be consented by [name] OT (Co-Investigator and Director of Rehabilitation at PowerBack).

Participants standardised evaluations for feasibility study

Before the VR training (A) all participants will be evaluated by a senior occupational therapist (OT). The OT will evaluate:

- UE FMA,
- Jebsen test of hand function [Jebsen 1969],
- bimanual activities CAHAI-9 [Barreca 2004]),
- UE active range of shoulder movement - goniometer,
- shoulder strength -wrist weights,
- grasp and pinch strength -dynamometer and pinch meter), and
- independence in ADLs (upper extremity functional index [Stratford et al, 2001]).
- Blood Pressure and Pulse.

Pre-experimental therapy, a neuropsychologist, blinded to the intervention, will perform the cognitive/emotive evaluations. We will assess:

- emotive state (via the Beck Depression Inventory II),
- verbal and visual attention (with the Neuropsychological Assessment Battery NAB),
- processing speed (with the Trail Making Test A [Heaton 1991] - TMT),
- verbal and visual learning and memory (with the Hopkins Verbal Learning Test, Revised (HVLN-R) [Brandt 2001] and the Brief Visuo-spatial Memory Test, Revised (BVMT-R) [Benedict 1997]), and
- executive function with the Trail Making Test B (TMT-B) and the NAB Executive Functioning Module.

The initial evaluations will serve as baseline for all participants. Subsequent to the VR training on the BAC system, all feasibility participants will be evaluated again (A) for motor impairments and function, cognitive and emotive state for indication of clinical benefit. These clinical evaluations will be performed at the PowerBack.

Inpatient experimental therapy for the feasibility study

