The first BAC system will be installed at PowerBack and 6 participants 5 to 10 days post CVA admitted to inpatient rehabilitation will be recruited. They will train for up to 3 weeks, every other day, totalling up to 12 rehabilitation session playing a series of integrative exercises. Each session will start with a baseline for arm reach in the horizontal and vertical plane, pronation/supination range, as well as grasp strength and finger extension. These baselines will be used to adapt each game to an individual participant's motor impairment level in a given day, making the games winnable. Games

will produce congratulatory feedback, designed to maximize motivation, giving the subjects a feeling of control over their therapy and of accomplishment.

To combat boredom, new games will be added, such that the number of available games will progress from 4 games for sessions 1-4 to 6 games for sessions 5-8, and 8 games for sessions 9-12. The characteristics of each game will change from week to week (for example later-stage games will use dual-tasking involving moving and grasping simultaneously). Subjects will have a choice of games to play from among those available and will know the level they had achieved in a particular game.

The VR training will progress from 15 minutes/session of actual play (sessions 1-4), to 20 minutes (sessions 5-8) to 30 minutes (sessions 9-12). The BAC will be used in uni-manual mode providing training to the affected UE in sessions 1-4, and in bimanual mode for sessions 5-12. Furthermore, grasp and shoulder training will progress from no grasping required in sessions 1-4, to momentary grasping needed to play in sessions 5-12. Towards the end of training each session should induce >600 repetitions/arm, an amount consistent with inducing brain plasticity [Nudo 1997]. Subjects will play while supported by the BAC table in horizontal position. At the discretion of the therapist in the room, if moderate to mildly impaired participants tolerate, the table may be tilted up to 10 degrees.

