Before the start of a session the participant's blood pressure and pulse will be measured, to make sure it is safe to train that day. After the half-time mark is reached, the BAC system will automatically pause the session and ask for another reading of blood pressure and pulse. Once the prescribed game time is reached for a session, the game time is automatically ended by the system and the Therapist prompted to do one more blood pressure and pulse readings.

A remote database will store game performance data and allow access by the researchers following subject compliance to protocol and game performance progression. Subjects will be given the opportunity to make up any missed sessions.

At the end of sessions 4, 8 and 12 subjects will fill online subjective evaluation form rating their experience on the system. When logged over time these evaluations will give a measure of the subject's perceived value of the experience. Technology acceptance will also be gaged based on adherence to protocol.

At the end of Session 12 of a given subject, the OT will fill his/her custom evaluation form of the BAC system. The therapist will rate the ease of setting up sessions, the perceived benefit in terms of reduced work load, ease of notes entering, number of technical problems encountered, appropriateness of training intensity and overall satisfaction. Therapists will also have a log-book for noting session specific issues. Participants in the feasibility evaluation will not be paid.

Subsequent to the training of the 6 subjects at PowerBack, and based on their feedback we may fine-tune the BAC systems prior to deployment to the Kessler Foundation for the randomized control study.

Outcomes of feasibility study on individuals early post-stroke

Primary outcomes:

v. 7/8/2018

- The main motor outcome measure will be the FMA UE score, and success will be a group average score increase of 10 points or more, compared to baseline.
- The main outcome for the cognitive domain will be executive function improvement measured by Trail Making Test B (TMT-B) and the NAB Executive Functioning Module.

Secondary outcomes:

In the motor impairment domain secondary outcomes will be:

- increased arm range in pronation/supination (based on new games we will develop);
- grasp strength increase;
- finger extension range increase,
- increase in UEFI;

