- bimanual training to improve CAHAI 9 scores (by at least 6 points), reflecting more ADL independence in tasks that are requiring both arms. The progression in ADL independence will be indicative of transfer to function.
- Other secondary outcomes will be changes in therapeutic game scores,
- change in game duration (indicative of reduction in task completion time)
- change in play intensity (number of arm movement repetitions/minute);
- participants' subjective evaluation scores for ease of use of the BAC, and overall system rating.

In the cognitive domain, secondary outcomes will be:

- improved focus,
- better verbal and visual memory.

In the emotional domain, we will evaluate the depression scores as measured by the Becks Depression Inventory II standardized test. We will consider success an average group reduction of 5 points in the severity of depression.

Pilot Feasibility Study for BrightBrainer use by individuals with PD (BCI/CCIT site)

This will be an ABA protocol. Measures will be taken pre- outpatient therapy (A), during outpatient experimental therapy on BrightBrainer (B), and post inpatient therapy (A).

Subject Recruitment

[name] OT will reach out to PD support groups in NJ to publicize the pilot. She will use the publicity flier developed for this purpose. Those interested will be consented at CCIT.

Subject standardised evaluations for pilot feasibility study on individuals with PD.

- the Canadian Occupational Performance Measure (Law et al., 2005)
- the Upper Extremity (UE) dual task function test. UE dual task function test involves repeated upper extremity elbow flexion with a gyroscope to measure repetitions and angular velocity with an added cognitive task such as counting backwards by seven or counting months of the year backwards (Toosizadeh et al., 2016)
- Timed Up and Go Cognitive (Shumway-Cook, Brauer, & Woollacott, 2000),
- cognitive measures of Trail making test (Reitan & Wolfson, 1994)

- Stroop test (Hsieh, Chen, Wang, & Lai, 2008).
- Upper extremity specific measures of Nine Hole Peg Test (Mathiowetz & Kashman, 1985)
- Modified functional reach test (Smithson, Morris, & Iansek, 1998),
- Parkinson's Disease Activities of Daily Living Scale (Hobson, Edwards, & Meara, 2001) and

Movement Disorder Society Unified Parkinson's Disease Rating Scale (Goetz et al., 2007)

Outpatient experimental therapy for individuals with PD

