- pinch strength (pinch-meter)bimanual activities (Chedoke Inventory -9) [Barreca 2000]. The need to evaluate both UEs stems from the nature of BAC bimanual training and from our inclusion of subjects who may be bilaterally affected by their first CVA.

Emotional & Neuropsychological evaluations

- The neuropsychologist will perform the cognitive/emotive evaluations. We will assess
- emotive state (via the Beck Depression Inventory II)
 - verbal and visual attention (with the Neuropsychological Assessment Battery NAB)
 - processing speed (with the Trail Making Test A [Heaton 1991] - TMT)
 - verbal and visual learning and memory (with the Hopkins Verbal Learning Test, Revised (HVLTR) [Brandt 2001])
 - Brief Visuo-spatial Memory Test, Revised (BVMT-R) [Benedict 1997])
 - executive function with the Trail Making Test B (TMT-B) and the NAB Executive Functioning Module.

The initial evaluations will serve as baseline for all participants. Subsequent to the inpatient VR training, all participants will be evaluated again for cognitive and emotive state for indication of clinical benefit. Subjects who transition to home will be evaluated again at the start of their outpatient rehabilitation. All subjects will be evaluated again for cognitive and emotive state at the end of their outpatient therapy. For subjects who skip home rehabilitation and transition directly to outpatient training, the measures at discharged from inpatient rehabilitation will be considered as baseline for start of outpatient training. To minimize test learning effects we will use alternate test forms for NAB tests, as well as reliable change formulas for all other forms [Jacobsen and Truax, 1991].

Inpatient and outpatient experimental therapy for the control study at Kessler Foundation

All subjects, regardless of group randomisation, will continue their standard of care rehabilitation (physical therapy, occupational therapy, speech and language therapy and cognitive training). All subjects, regardless of randomization, will have the same duration of therapy. Specifically, subjects randomised in the control group will have an added duration of standard of care rehabilitation equal to the experimental group training duration on the BAC.

Experimental group

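### The uncontrolled six-person feasibility study reads a cognitive retest as a sign of benefit, but the protocol's safeguards against test learning are written only for the RCT

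*Protocol*

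**What the plan says.** The design is set out in the Protocol under *Feasibility Study (PowerBack Rehabilitation)*: "This will be an ABA protocol, with measures taken pre- (A), during experimental therapy (B) and post-intervention (A"). There is one group. The section on inpatient experimental therapy for this study states that "6 participants 5 to 10 days post CVA admitted to inpatient rehabilitation will be recruited", and training lasts up to 3 weeks.

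Under *Outcomes of feasibility study on individuals early post-stroke*, the cognitive primary outcome reads: "The main outcome for the cognitive domain will be executive function improvement measured by Trail Making Test B (TMT-B") and by the NAB Executive Functioning Module. No amount of change is attached. Nearby outcomes do carry one. For the FMA, "success will be a group average score increase of 10 points or more, compared to baseline". For the Beck inventory, "We will consider success an average group reduction of 5 points in the severity of depression". CAHAI-9 has a 6-point figure.

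Under *Participants standardised evaluations for feasibility study*, the purpose of the retest is explicit: "all feasibility participants will be evaluated again (A) for motor impairments and function, cognitive and emotive state for indication of clinical benefit". That section does not say which test forms are used at retest.

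The RCT section on emotional and neuropsychological evaluations does: "To minimize test learning effects we will use alternate test forms for NAB tests". The same sentence adds reliable change formulas for all the other tests, which covers TMT-B. *Data Analysis and Data Monitoring* describes a repeated measures ANOVA of pre-training against post-training results.

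**The concern.** Three influences other than the device can raise the second score: having taken the test before, spontaneous recovery in the first weeks after stroke, and the standard rehabilitation that continues throughout. All three push in the direction the outcome counts as improvement, and a single group gives no means of separating them from the device.

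The protocol recognises the first two, but only for the RCT. It specifies the form rule and reliable change formulas there, and says under *Control study Outcomes* that the RCT recovery curves should help distinguish natural recovery from training gains. So the safeguards are written for the study that has a control group and not for the one that has none.

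At stake is how a named primary outcome is interpreted. The purpose section says this study will give an initial indication of clinical benefit, including cognitive function, and the RCT takes over the same cognitive outcome.

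**Working it through.** **No figure to reproduce.** The protocol gives no alpha, power, SD, or expected practice or recovery gain for this outcome. The calculation below illustrates the size of the problem under stated assumptions.

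**Inputs from the protocol.** n = 6, one group, one cognitive evaluation before and one after training. Sessions are every other day, up to 12. Eleven such sessions fit in 21 days, and a twelfth falls on day 1 + 2 × 11 = 23, so the retest interval is about 3 weeks.

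**Assumed.** The device has no effect. Practice plus recovery and usual care shifts the score by d, measured in SDs of the change score in the better direction, with d = 0, 0.5 or 0.8. Change scores are normal.

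**Reading A: the group mean on one test moves the right way.** P = Φ(d√6).

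- d = 0: Φ(0) = 50%
- d = 0.5: Φ(1.22) = 89%
- d = 0.8: Φ(1.96) = 97.5%

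**Reading A with two tests.** Let the correlation between the two change scores run from 0 to 0.8 (assumed).

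| d | both means improve | at least one improves |
|---|---|---|
| 0 | 25% to 40% | 60% to 75% |
| 0.5 | 79% to 84% | 94% to 99% |
| 0.8 | 95% to 96% | 99% to above 99% |

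**Reading B: a significant pre-post improvement is required.** With two time points and one group, repeated measures ANOVA is the paired t test on 5 degrees of freedom. Take two-sided 0.05 (assumed, since the protocol gives no alpha) and noncentrality d√6. The chance of a significant result in the direction of improvement is:

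- d = 0: 2.5%
- d = 0.5: 17%
- d = 0.8: 36%

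**What the two readings share.** Under B the error is at its nominal level when there is no practice or recovery. It then rises to about 7 times that level at d = 0.5 (16.9 / 2.5 = 6.8) and 14 times at d = 0.8 (35.6 / 2.5 = 14.2). The pre-post ANOVA does not remove the shift; it only asks that the shift be larger relative to noise. Both readings therefore point the same way, at very different levels.

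**The case against.** The strongest reply is that the protocol never says any positive mean change counts as success. It attaches success to the FMA and Beck outcomes; for cognition it names a domain and two tests. A reader might infer that improvement of any size suffices, and so that the outcome would appear positive half the time or more with an inert device. The text does not support this. Having no success rule is different from having a lax one, the stated analysis is a repeated measures ANOVA, and a criterion may sit in an SAP that is not at hand. If both tests must improve and d = 0, even the mean-change reading falls below one half. This part of the reply stands, which is why both readings are shown.

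A reader might also infer that the same NAB form will be reused. The feasibility section is silent on forms, so the supportable statement is that none is specified. Nor can one say that practice and recovery will produce an apparent benefit, only that they can.

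It is also fair that the study has six participants, claims only an initial indication, and is followed by fine-tuning of the device from participants' feedback. No decision to proceed and no RCT sample size is tied to the cognitive result. Confounding by recovery is inherent in any such pilot. This limits the consequence but does not remove the point: the protocol still calls the outcome primary and the retest an indication of benefit. The choice of retest form is also a data-collection step. If the same form were given twice, no later analysis of six uncontrolled participants could isolate the practice gain.

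**Conclusion.** The point holds in a limited form. The feasibility study's cognitive primary outcome is an uncontrolled pre-post change without a threshold, read as an indication of benefit, and the learning-effect safeguards the protocol itself considers necessary are not specified for it. Practice, recovery and standard care can make the result read as benefit.

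The size is conditional on the assumed 0 to 0.8 SD shift, for which the protocol gives no figure, and on the criterion used. The significance figures also assume a two-sided 0.05 level. These probabilities do not measure what the fix would gain: d combines practice with recovery and usual care, and the safeguards address only practice. That is why the wording of the interpretation has to change as well as the test forms.

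A reader might assume that the RCT already supplies a controlled answer on cognition. It has a control group, but its outcome section repeats the same wording without a threshold, and the analysis section describes only a pre-post comparison. No between-group cognitive comparison is stated. This should be corrected, but it is not critical to the trial.

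**What to change.** 1. In *Participants standardised evaluations for feasibility study*, apply the whole of the RCT's learning-effect sentence: an alternate NAB form at the post-training evaluation, and reliable change formulas for TMT-B and the other tests.
2. In the feasibility primary outcomes, report the mean pre-post change in TMT-B and in the NAB Executive Functioning Module with 95% confidence intervals, labelled descriptive. State that the change includes practice, recovery and usual care and is not attributed to the BAC.
3. In *Data Analysis and Data Monitoring*, state an experimental-versus-control comparison for the RCT's cognitive outcome, and say that any claim of cognitive benefit rests on it.

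The cost is protocol wording. Alternate NAB forms and reliable change formulas are already planned for the RCT. The downside is that the feasibility study can no longer claim cognitive benefit from a bare pre-post gain.

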measures taken during outpatient therapy on BAC (B), and post-outpatient treatment (A).

Subject Recruitment

20 elderly 5 days or more post-CVA admitted to Kessler Institute for Rehabilitation/Kessler Foundation) for inpatient rehabilitation will be recruited. Subjects will be pre-screened through a standardized questionnaire and MoCA screening. We expect to screen at least 70 potential subjects, also trying to determine candidates who will continue outpatient rehabilitation at Kessler Foundation. Those who met inclusion criteria will be consented by [name] MD or [name] (Co-Investigators). The 20 recruited subjects will subsequently be randomised equally into an experimental group (n=10) and a control group (n=10).

We will also recruit the 20 caregivers of the experimental and control subjects. The caregivers will provide feedback on the subjects during the outpatient component of their therapy, every 4 weeks. We will be looking for changes in independence in activities of daily living, cognition and mood that the caregivers will report, as well as self-reported outcomes by the subjects. The feedback will be using the Stroke Impact Scale [Duncan et al. 2002] and the Upper Extremity Functional Index (UEFI) [Stratford 2001] standardized questionnaires, as well as free form communication with researchers.

Subject standardised evaluations for control study on early sub-acute post stroke

Both experimental and control groups will undergo standardised evaluations for motor function/impairment, cognition and emotive states. All subjects will be evaluated before, and after their in-patient rehabilitation. Those patients who transition to home rehabilitation will be evaluated again before commencing outpatient rehabilitation, while those who transition directly to outpatient rehabilitation will not. All subjects will be evaluated again at the completion of their outpatient therapy. All clinical evaluations of the control study subjects will be performed at the Kessler Kessler Foundation.

OT evaluations

An occupational therapist blinded to the treatment allocation will evaluate for motor impairment and function of both UEs. These evaluations are the following:

- Fugl Meyer Assessment (FMA)
- Jebsen test of hand function [Jebsen 1969]
- active range of shoulder, elbow and finger movement (goniometer)
- shoulder strength (wrist weights)
- range of forearm pronation/supination
- grasp strength (dynamometer)

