In the motor domain the session will train endurance (by increasing the length of training), strength (by modulating gravity loading and lifting arm off table), motor control (by requiring patients to follow prescribed paths), and movement speed (by inducing more arm repetitions per minute).

In the cognitive domain the cognitive load will gradually be increased by moving from uni-manual play (need to control only one avatar) to bimanual play (simultaneous control of two avatars). This will train split attention, task sequencing and dual tasking, something problematic for the elderly.

Control group

10 subjects in the control group will receive their standard of care intervention during inpatient rehabilitation post CVA. To this we will add an equal duration of standard of care to the experimental therapy (progressing from 15 minutes/session in sessions 1-4 to 30 minutes during the last inpatient session). In the outpatient period they will have an added duration of customary therapy. The added therapy will progress from 30 minutes/session at start of outpatient therapy to 45 minutes/session at the end, matching the experimental group training duration on the BAC.

Control study Outcomes

Primary outcomes

The primary outcomes for both groups will be those outlines in the Feasibility Study component of the project. The main motor outcome measure will be the FMA UE score, and success will be a group average score increase of 10 points or more, compared to baseline. The main outcome for the cognitive domain will be executive function improvement measured by Trail Making Test B (TMT-B) and the NAB Executive Functioning Module.

Secondary outcomes

The secondary outcomes for both groups will be those outlined in the Feasibility Study component of the project,

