- o **Data Analysis and Data Monitoring.** We will use repeated measures of ANOVA statistical analysis to look at the participants' data comparing pre-training conventional evaluation results with post-training results, to determine early indications of clinical benefit. We will also collect subjective evaluation questionnaires from each participant and from the occupational therapist (once post-training) on their impression of the system, its perceived benefits and shortcomings, its ease of use in a clinical setting. We will also collect data on Activities of Daily Living, using a standardised form, as well as data from caregivers so to gauge transfer of training to real life activities.

In order to gauge technology acceptance we will collect a subjective evaluation of the BAC from each participant in the experimental group. The scores (1 – least favourable outcome to 5 most favourable one) from each question will be averaged over the group. The BAC subjective evaluation forms will be collected twice (after 6 weeks of outpatient therapy and at end of outpatient therapy). By looking at the progression (or regression) of these scores, we will also be able to determine if ease of use of the technology increased with the accumulation of training sessions (or not).

All the data will be entered to the central data management system remotely.

- o **Data Storage and Confidentiality.** Each subject will have his/her name encoded such that the experimental and clinical measures will not log the participant's real name. The only mapping between the assigned encoded ID and the participant's real identity will be on the consent forms. These will be kept under lock by:

- 1) [name] OT and [name] for the participants early post-stroke PowerBack Rehabilitation;
- 2) [name] for the participants early post-stroke training at Kessler Foundation

The computerized data will be uploaded on a cloud secure database. Access to the database will only be granted to the research team, and will be password protected. Paper records involving the motor and cognitive evaluations as well as the subjective evaluation questionnaires will also be kept locked by [name] OT, [name], [name] (for the cognitive and emotive evaluations of the feasibility subjects) and [name] MD for the controlled trials subjects at Kessler Foundation.

- o **Transition from Research Participation.** Subjects will not have their standard of care or medication interrupted during participation.

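### The reliable change index cited against learning effects does not correct TMT-B for practice, so a pre-post reading of the main cognitive outcome would count practice gain as benefit

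*Protocol*

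**What the plan says.** All references are to the Protocol.

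- **Emotional & Neuropsychological evaluations (randomised study).** The battery assesses "executive function with the Trail Making Test B (TMT-B) and the NAB Executive Functioning Module". TMT-B is listed separately from the NAB module. Learning effects are dealt with in one sentence: "To minimize test learning effects we will use alternate test forms for NAB tests, as well as reliable change formulas for all other forms". The sentence cites Jacobson-Truax; no formula, expected practice gain or practice-corrected variant is given. After inpatient training, "all participants will be evaluated again for cognitive and emotive state for indication of clinical benefit".
- **Control study Outcomes, Primary outcomes.** The main cognitive outcome is "executive function improvement measured by Trail Making Test B (TMT-B) and the NAB Executive Functioning Module". It is carried over from the single-arm feasibility study and applied to both groups, with no threshold and no stated contrast between arms.
- **Data Analysis and Data Monitoring.** Repeated measures ANOVA is to be used, "comparing pre-training conventional evaluation results with post-training results, to determine early indications of clinical benefit".
- **Subject standardised evaluations for control study.** "Both experimental and control groups will undergo standardised evaluations for motor function/impairment, cognition and emotive states". On the number of tests: "Those patients who transition to home rehabilitation will be evaluated again before commencing outpatient rehabilitation", while those who go straight to outpatient care skip that test. Each subject is therefore tested three or four times.
- **Control study Outcomes, closing paragraph.** Recovery curves are meant to help tell natural recovery from gains due to the device. The paragraph is introduced as being about motor recovery.

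**The concern.** The protocol recognises that repeated cognitive testing produces learning and says how it will limit it. For the NAB tests the method, alternate forms, fits the purpose. For TMT-B it does not. A reliable change index asks whether one person's change is larger than measurement error would produce. It does not ask how much of that change comes from having taken the test before.

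Two things follow. First, a reader or analyst may believe that practice on TMT-B has been dealt with when it has not. Second, the outcome is worded as improvement and the analysis as pre-training against post-training results. If the conclusion were drawn that way, a faster TMT-B on retest could be reported as better executive function due to the device. The design already holds the remedy, since randomised controls take the same battery, but the text does not say that the cognitive conclusion rests on them.

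**Working it through.** The protocol gives no retest correlation, SD, practice gain or alpha for TMT-B, so there is no stated figure to reproduce. What follows is an illustration.

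**Inputs.** From the protocol: 10 per arm. Assumed: retest correlation r of 0.7 to 0.9; practice gain g of 0 to 0.5 baseline SD, equal in both arms; no true treatment effect; two-sided 5% level; normal scores with improvement coded positive.

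**Step 1, the index.** RCI = (x2 − x1) / (SD × √(2(1 − r))). There is no term for expected gain. With a mean gain of g SD, the mean RCI is g / √(2(1 − r)), so practice is rescaled but not removed. At r = 0.8 the divisor is √0.4 = 0.632, and g = 0.2, 0.3 and 0.5 give mean RCI 0.32, 0.47 and 0.79. The chance that a person is flagged as improved is 1 − Φ(1.96 − mean RCI).

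**Step 2, a within-arm pre-post test.** Paired t-test, n = 10, 9 df, noncentrality g / (√(2(1 − r)) / √10). At r = 0.8 the standard error is 0.632 / √10 = 0.200, so g = 0.2, 0.3 and 0.5 give noncentrality 1.0, 1.5 and 2.5.

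| r | g (SD) | Index flags a person as improved (nominal 2.5%) | Within-arm test significant (nominal 5%) |
|---|---|---|---|
| 0.8 | 0 | 2.5% | 5.0% |
| 0.8 | 0.1 | 3.6% | 7.3% |
| 0.8 | 0.2 | 5.0% | 14.6% |
| 0.8 | 0.3 | 6.9% | 26.9% |
| 0.8 | 0.5 | 12.1% | 60.6% |
| 0.7 | 0.2 | 4.4% | 11.3% |
| 0.7 | 0.5 | 9.4% | 44.6% |
| 0.9 | 0.2 | 6.5% | 24.5% |
| 0.9 | 0.5 | 20.0% | 88.1% |

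**Step 3, a practice-corrected index.** Subtracting the expected gain, (x2 − x1 − g) / (SD × √(2(1 − r))), returns the flag rate to 2.5%, provided g is known.

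**Step 4, a between-arm contrast.** In 100,000 simulated trials at r = 0.8 with equal gain in both arms, the baseline-adjusted difference and the difference in change each reject in about 5%, with bias 0.00.

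**Step 5, precision at r = 0.8.** Within-arm change: 0.200 SD. Difference in change: 0.632 × √(2/10) = 0.283 SD. Baseline-adjusted difference: √(1 − 0.64) × √(2/10) = 0.268 SD (0.277 in simulation, because the slope is estimated).

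**Step 6, unequal numbers of tests at the end of outpatient therapy.** Assume that a fourth test adds 0.2 SD. If 5 of 10 in each arm take it, bias is 0.00. If 8 against 2 take it, bias is 0.2 × (0.8 − 0.2) = 0.12 SD and the baseline-adjusted contrast rejects in about 7%. If 10 against 0, bias is 0.20 SD and it rejects in about 10%.

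**The case against.** The strongest reply is that the harm depends on a reading the protocol does not fix. Repeated measures ANOVA can carry a group-by-time term, the analysis paragraph serves the single-arm feasibility study as well as the randomised one, and a separate analysis plan may name the contrast. The cognitive outcome has no success threshold, and the analysis claims only early indications. This stands: a reader might infer that the trial is bound to test TMT-B within arms and declare a false benefit, and the document does not say so. An unseen analysis plan would not, however, make the sentence about learning effects correct. That sentence is a positive statement about a named method.

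A second reply is that no formula is printed and a practice-corrected variant may have been intended. That is possible, but none is named and no expected gain is given. The point here rests on the algebra of the standard index of that name.

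A third is that every input to the figures is assumed. That is true, and at a gain of 0.1 SD the effect is small (7.3% against 5% at r = 0.8).

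A reader might also infer that the protocol would credit natural recovery to the device. That goes beyond the error in the learning-effects sentence, and the outcomes section does plan to separate natural recovery from training gains, though for motor recovery and not for practice on cognitive tests.

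**Conclusion.** The concern holds in a limited form. That the standard cited index does not limit learning effects on TMT-B follows from its definition and needs no assumption about size. The consequence is conditional: if the cognitive result is read as pre-post improvement, as the outcome and analysis wording suggests, practice gain enters it. With no true effect, r = 0.8, 10 per arm and a shared gain of 0.2 to 0.5 SD, the index flags 5% to 12% of individuals against 2.5%, and a within-arm test is falsely positive in 15% to 61%. A between-arm contrast stays at about 5%, and all rates are nominal if there is no gain. The NAB half of the outcome is less exposed because it has alternate forms.

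It might be inferred that the deciding visit must move to the end of inpatient therapy, when everyone has been tested twice. The figures do not require it: balanced extra testing gives no bias, and even an 8 against 2 split raises rejection only to about 7%. This should be corrected, but it does not undermine the design.

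**What to change.** **Emotional & Neuropsychological evaluations.** Keep the alternate NAB forms. Remove the claim that the cited index minimises learning effects, or replace it with a named practice-corrected variant and state where its expected gain comes from. If an uncorrected index is kept, describe it as a measurement-error threshold for individual change and report it by arm.

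**Control study Outcomes; Data Analysis and Data Monitoring.** State that the TMT-B and NAB conclusion rests on the between-arm difference adjusted for baseline, or on the between-arm difference in change, at the visits already planned. Present within-arm change as descriptive. Report the number of test administrations (three or four) by arm alongside the end-of-outpatient contrast.

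**Cost.** These are wording changes that use data already to be collected, with no change of visit. The price is precision: a standard error of about 0.27 to 0.28 SD against 0.20 SD for a within-arm change at r = 0.8, so with 10 per arm a modest true effect may not be distinguishable from none. A practice-corrected index would also need an expected gain that the protocol does not now supply.
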